16.1 Definitions

These definitions reflect the minimal regulatory obligations; specific protocol requirements might apply in addition.

AE: An Adverse Event is defined as "any untoward medical occurrence in a patient or clinical investigation subject administered a pharmaceutical product and which does not necessarily have to have a causal relationship with this treatment". An adverse event can therefore be any unfavorable and unintended signs (such as rash or enlarged liver), symptoms (such as nausea or chest pain), an abnormal laboratory finding (including results of blood tests, x-rays or scans) or a disease temporarily associated with the use of the protocol treatment, whether or not considered related to the investigational medicinal product.

AR: An Adverse reaction of an investigational medicinal product is defined as “any noxious and unintended response to a medicinal product related to any dose administered”.

All adverse events judged by either the reporting investigator or the sponsor as having a reasonable causal relationship to a medicinal product qualify as adverse reactions. The expression reasonable causal relationship means to convey in general that there is evidence or argument to suggest a causal relationship.

UAR: An Unexpected Adverse Reaction is “any adverse reaction, the nature, or severity of which is not consistent with the applicable product information” (e.g. investigator's brochure for an unapproved investigational product or summary of product characteristics (SmPC) for a marketed product).

When the outcome of the adverse reaction is not consistent with the applicable product information this adverse reaction should be considered as unexpected.

Severity: The term “severe” is often used to describe the intensity (severity) of a specific event (as in mild, moderate or severe, or as described in CTC grades); the event itself, however, may be of relative minor medical significance (such as severe headache). This is not the same as “serious,” which is based on patient/event outcome or action criteria usually associated with events that pose a threat to patient’s life or functioning. Seriousness (not severity) serves as a guide for defining regulatory reporting obligations.

SAE: A Serious Adverse Event is defined as any untoward medical occurrence or effect in a patient, whether or not considered related to the protocol treatment, that at any dose:

- results in death
- is life-threatening (i.e. an event in which the subject was at risk of death at the time of event; it does not refer to an event which hypothetically might have caused death if it were more severe)
- requires inpatient's hospitalization or prolongation of existing inpatients’ hospitalization
- results in persistent or significant disability or incapacity
- is a congenital anomaly or birth defect
- results in any other medically important condition (i.e. important adverse reactions that are not immediately life threatening or do not result in death or hospitalization but may jeopardize the patient or may require intervention to prevent one of the other outcomes listed above), e.g. secondary malignancy, AE as a result of an overdose

SAR: A Serious Adverse Event (SAE) which is considered related to the protocol treatment is defined as a **Serious Adverse Reaction**

SUSAR: Suspected Unexpected Serious Adverse Reaction.

SUSARs occurring in clinical investigations qualify for expedited reporting by the sponsor to the appropriate Regulatory Authorities in accordance with Directive 2001/20/EC and with respective national regulations.

Inpatient or in-patient's hospitalization: A patient who is admitted to a hospital or clinic for at least one overnight stay.

16.2 Exceptions

The following situations are not considered to be SAEs and should not be reported on the SAE form:

- Elective hospitalization for pre-existing conditions that have not been exacerbated by trial treatment
- A hospitalization which was planned before the patient consented for study participation and where admission did not take longer than anticipated

- Medical or surgical procedure (e.g. endoscopy, appendectomy); the condition that leads to the procedure is an (S)AE
- Situations where an untoward medical occurrence did not occur (social and/or convenience admission to a hospital, palliative care, rehabilitation, overdose without occurrence of an adverse event)
- Anticipated day-to-day fluctuations of pre-existing disease(s) or condition(s) present or detected at the start of the study that do not worsen.

By EORTC convention, clinical events related to the primary cancer progression are not to be reported as SAEs, even if they meet any of the seriousness criteria from the standard SAE definition, unless the event is more severe than expected and therefore the investigator considers that their clinical significance deserves reporting.

16.3 Severity assessment

The severity of all AEs (serious and non-serious) in this trial should be graded using CTCAE v3.0 (https://ctep.cancer.gov/protocoldevelopment/electronic_applications/docs/ctcae3.pdf).

16.4 Causality assessment

The investigator is obligated to assess the relationship between protocol treatment and the occurrence of each SAE following definitions in this table:

Relationship to the protocol treatment	Description
UNRELATED	There is no evidence of any causal relationship to the protocol treatment
LIKELY RELATED	There is (some) evidence to suggest a causal relationship to the protocol treatment and influence of other factors is unlikely or absent.
NOT ASSESSABLE	There is insufficient or incomplete evidence to make a clinical judgment of the causal relationship to the protocol treatment.

The investigator will use clinical judgment to determine the relationship. Alternative causes, such as natural history of the underlying diseases, medical history, concurrent conditions concomitant therapy, other risk factors, and the temporal relationship of the event to the protocol treatment will be considered and investigated.

The decision will be recorded on the Serious Adverse Event form, if necessary with the reasoning of the principal investigator.

16.5 Expectedness assessment

The expectedness assessment is the responsibility of the *sponsor* of the study, unless otherwise specified in the Group specific appendix. The expectedness assessment will be performed against the following RSI (reference safety information):

- For Temozolomide: RSI Section 4.8 of Summary of Product Characteristics (SmPC) which can be found on the European Medicines Agency's website.

16.6 Reporting procedure for investigators

This procedure applies to all Serious Adverse Events (SAE) occurring from the time a subject is randomization until 30 days after last protocol treatment and to any SAE that occurs outside of the SAE detection period (after the 30-days period), if it is considered to be likely related to the investigational product or study participation.

Randomization till 30 days after last protocol treatment:	All SAEs
From day 31 after last protocol treatment:	Only related SAEs

All reporting must be done by the principle investigator or authorized staff member (i.e. on the signature list) to confirm the accuracy of the report.

All SAE data must be collected on the study-specific SAE form.

All SAEs must be reported immediately and no later than 24 hours from the time the investigator or staff became aware of the event.

All SAE-related information needs to be provided in English.

All additional documents in local language must be accompanied by a translation in English, or the relevant information must be summarized in a follow-up SAE report form.

Investigators participating through **EORTC** must fax/e-mail all SAE-related information to:

EORTC Pharmacovigilance:

[contact]

E-mail: [contact]

Investigators participating through **non-EORTC groups** should consult their **group specific appendix** for further details on the reporting of Serious Adverse Events.

To enable the EORTC to comply with regulatory reporting requirements, all initial SAE reports should always include the following minimal information: an identifiable patient (SeqID), a suspect medicinal product if applicable, an identifiable reporting source, the description of the medical event and seriousness criteria, as well as the causality assessment by the investigator. Complete information requested on the SAE form of any reported serious adverse event must be returned within 7 calendar days of the initial report. If the completed form is not received within this deadline, the EORTC Pharmacovigilance will make a written request to the investigator.

Queries sent out by the EORTC Pharmacovigilance need to be answered within 7 calendar days.

All forms need to be dated and signed by the principle investigator or any authorized staff member (i.e. on the signature list).

16.7 Reporting to investigators and competent authorities

The EORTC Pharmacovigilance will forward all SAE reports within 24 hours of receipt to the appropriate persons within the EORTC Headquarters, the EORTC Study Coordinator and the pharmacovigilance contact at Merck.

All SUSARs will additionally be notified to all EORTC participating investigators, Ethics committees (of EORTC centers) and all central Data Managers of all Cooperating Groups.

The EORTC Pharmacovigilance will take in charge the expedited reporting to all Competent Authorities and EVCTM, whenever applicable.

The EORTC Pharmacovigilance will prepare the Annual Safety Report/ Development Safety Update Report and distribute it to the central Data Managers of all Cooperating Groups, the European Competent Authorities and Merck.

Every Group shall be responsible for distribution of Safety information to their investigators and respective Ethics Committees, whenever applicable.

16.8 Pregnancy reporting

Pregnancy occurring during a patient's participation in this trial, although not considered an SAE, must be notified to the EORTC Pharmacovigilance of the respective group Data Center within the same timelines as an SAE (within 24 hours) on a Pregnancy Notification Form. The outcome of a pregnancy should be followed up carefully and any abnormal outcome of the mother or the child should be reported. This also applies to pregnancies following the administration of the investigational product to the father prior to sexual intercourse.

- Any pregnancy in a female subject or in a female partner of a male subject diagnosed during the treatment period or within 30 days after last study treatment administration must be reported to the EORTC Pharmacovigilance of the respective group Data Center
- This must be reported within 24 hours of first becoming aware of the event by fax, to EORTC Pharmacovigilance on a Pregnancy Notification Form/Fax
- If a Serious Adverse Event (SAE) occurs in conjunction with the pregnancy, please also complete an SAE form as explained in the SAE chapter
- Upon notification of a pregnancy, it will be the responsibility of the pharmaceutical company, Merck, to follow-up the development and outcome of the pregnancy.

17 Quality assurance

17.1 Control of data consistency

Data forms will be entered into the database of the EORTC Headquarters by a double data entry procedure. Computerized and manual consistency checks will be performed on newly entered forms; queries will be issued in case of inconsistencies. Consistent forms will be validated by the data manager. Inconsistent forms will be kept "pending" until resolution of inconsistencies.

17.2 Audits

The EORTC is responsible for the performance of the EORTC investigators.

The investigator, by accepting to participate in this protocol, agrees that EORTC, any third party (e.g. a CRO) acting on behalf of the EORTC, or any domestic or foreign regulatory agency, may come at any time to audit or inspect their site and all subsites, if applicable.

This audit consists of interviews with the principal investigator and study team, review of documentation and practices, review of facilities, equipment and source data verification.

The investigator will grant direct access to paper and/or electronic documentation pertaining to the clinical study (e.g. CRFs, source documents such as hospital patient charts and investigator study files) to these authorized individuals. All site facilities related to the study conduct could be visited during an

audit (e.g. pharmacy, laboratory, archives ...). The investigator agrees to co-operate and provide assistance at reasonable times and places with respect to any auditing activity.

If applicable, the company(ies) supplying the study drug(s) may have access to anonymized data but will not have access to source documents.

If a regulatory authority inspection is announced, the investigator must inform the EORTC Headquarters Compliance and Audits immediately (contact at: [contact]).

In this way EORTC can provide support in preparing and/or facilitating the inspection. EORTC representatives/delegates may also attend the inspection.

17.3 External review of histology and molecular diagnosis

17.3.1 Central review of histology

Samples shipments should be addressed to [name] (see section 17.3.3 for instructions). The central pathology review will be carried out by [name] and [name].

For the review, material embedded in paraffin must be sent to the above laboratory (same block will be used for the determination on 1p/19q, see section 17.3.3).

17.3.2 Central review of molecular diagnosis

Eligible for this study are patients with a histological diagnosis of an anaplastic astrocytoma, anaplastic oligoastrocytoma and anaplastic oligodendroglioma, without combined 1p/19q loss. Patients can be entered into the study either based on the local diagnosis or on central histology review and 1p/19q assessment. Centers must decide prior to the site initiation whether they will include patients based on local or on central histology and 1p/19q diagnosis.

Different techniques are available to assess loss of 1p and 19q (FISH, LOH, array CGH). Only centers that fulfill minimum quality requirements for 1p/19q testing and that are cleared by the EORTC Headquarters will be allowed to enter patients based on local diagnosis (see Appendix J). This must be determined prior to study activation by the EORTC datacenter and the study coordinator. Tumors from patients from centers that use central 1p/19q testing for eligibility assessment will simultaneously undergo histological review; patients are only eligible if at least one of the two central reviewers has confirmed the histological diagnosis and in the absence of combined 1p/19q loss.

To allow stratification of the patients according to MGMT status immediate post-surgery shipping of tumor material together with the required blood samples is an absolute requirement. **This also concerns tumor material from patients from centers that enter patients based on local 1p/19q testing.**

Stratification for MGMT status will be either 'methylated', 'non-methylated' or 'undeterminate'. Patients in whom MGMT status cannot be determined because of insufficient material, material not timely received etc will still be eligible for the study (and will be stratified for MGMT status as 'undeterminate').

Both the 1p/19q testing and the MGMT promoter methylation determination are essential for the study. The submission of tissue for these assays is therefore **mandatory**. The procedures for Europe are explained below. For non-European centers, a similar procedure is covered by Group Specific Appendices.

For patients that are included in the trial based on local determination the histological and molecular diagnosis will be centrally reviewed. Thus, for all patients 1p/19q status will be centrally assessed as part of the trial.

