1.1.2 Concomitant and adjuvant temozolomide in anaplastic glioma

The recent large randomized EORTC study 26981-22981/NCI-C CE3 showed that combined radiotherapy and temozolomide chemotherapy provides a superior outcome for patients with newly diagnosed glioblastoma as compared to adjuvant treatment with radiotherapy only.(Ref. 11) Correlative studies suggest that the benefit of combined alkylating agent chemotherapy and radiotherapy may be limited to patients whose tumors have a methylated (and thus silenced) MGMT gene promoter (Ref. 12). It is however far from clear that these results can be extrapolated to anaplastic glioma without 1p/19q loss.

Both toxicity and efficacy issues may be different for anaplastic glioma as compared to glioblastoma multiforme. Reviews of old RTOG/ECOG studies suggested a decreased survival in more aggressively treated anaplastic astrocytoma patients (Ref. 13). These data were obtained from historical comparisons over several trials, so the conclusions should be viewed with caution. Similarly though, in contrast to the reported 40-50% response rates to temozolomide if given prior to irradiation in newly diagnosed

glioblastoma, trials of pre-irradiation chemotherapy in anaplastic glioma yielded disappointing response rates, with only 17% to 30% of patients responding. (Ref. 14, Ref. 15, Ref. 16, Ref. 17) Radiotherapy may cause delayed neurological side-effects, in particular a subacute leuko-encephalopathy with mental slowing, memory disturbances, gait disorder and micturation problems. It is at present not known whether combined modality treatment with radiotherapy and temozolomide increases delayed neurotoxicity in patients with longer survival. The study of combined modality treatment in glioblastoma did not explore whether this increased late toxicities. Other treatments in which radiotherapy to the brain was combined with chemotherapy (e.g., primary CNS lymphoma) do suggest however that there may be a real risk. This becomes an even more relevant question in patients with a better prognosis who are at risk of developing these toxicities over a longer period of time.

Thus, it cannot be taken for granted that approaches leading to a better outcome in glioblastoma will also provide a superior outcome in anaplastic astrocytoma.

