8.1 Statistical design

8.1.1 Sample size

This is a 2 by 2 factorial design with Overall Survival as the primary endpoint when comparing:

- Patients receiving RT alone or RT + adjuvant TMZ to those receiving RT & concurrent TMZ or RT & concurrent TMZ + adjuvant TMZ.

[Question I: test for superiority of the concurrent TMZ chemotherapy]

- Patients receiving RT alone and RT & concurrent TMZ to those receiving RT + adjuvant TMZ or RT & concurrent TMZ + adjuvant TMZ.

[Question II: test for superiority of the adjuvant TMZ chemotherapy]

The hypotheses are the following:

- In the EORTC trial 26951 for Anaplastic Oligodendroglioma and Oligoastrocytoma tumors, patients with no combined 1p/19q LOH treated by RT alone had a median survival of 24 months. In the EORTC trial 26882 for Anaplastic Astrocytoma, patients treated by RT alone had a median survival of 24 months.
- No interaction is anticipated between the concurrent and adjuvant temozolomide treatment that are assumed to contribute equally to the survival improvement.
- In the EORTC trial 26981, comparing RT & Concurrent TMZ + adjuvant to RT alone, the estimated Hazard Ratio was 0.63 and its 95% Confidence Interval [0.52-0.75].

The following table summarizes the statistical parameters of the design. A Hazard Ratio (HR) of 0.775 is assumed for both questions.

RT		No adjuv CT (median OS)	Adjuv CT (median OS)	Question I	
				Median OS	HR
No conc CT		24 m	31 m	(24+31)/2=27.5	0.775
Conc CT		31 m	40 m	(31+40)/2=35.5	
Question II	Median OS	27.5	35.5		
	HR	0.775			

For both questions, to detect a reduction of the risk of death of 22.5%, based on a two-sided logrank test, at an overall significance level of 5% and a power of 83%, a total of 534 events are needed. With an estimated accrual rate of 150 patients per year, a total of **748** patients should be recruited within approximately 5 years. A minimum follow-up of 2 ½ years will be needed to observe the required number of events. One interim analysis for efficacy is planned when 41% of the events have been observed (219). To perform this interim look, 11 additional events are necessary. Power of the trial was slightly increased in order to compensate for the loss of information due to patients dropping out before starting the adjuvant treatment. It is estimated that 10% of the patients will fail during or within the month following radiotherapy.

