8.1.2 Randomization and stratifications

Patients will be centrally randomized (for practical details, see chapter on registration / randomization procedure). A minimization technique will be used for random treatment allocation stratifying by:

- Institution,
- WHO Performance Status (0 vs >0),
- Age (≤ 50 vs > 50),
- The presence of 1p LOH only (yes vs no) ,
- The presence of oligodendroglial elements (yes vs no) and
- MGMT promoter methylation status (methylated vs unmethylated vs indeterminate).

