8.2.4.2 Pre-planned exploratory analyses

In addition to the questions, pairwise comparisons of overall survival and progression-free survival between the three chemotherapy arms and the radiotherapy alone arm will be performed.

All comparisons will also be performed in each stratum of the following covariates: MGMT promoter methylation, 1p and 19q LOH and histological diagnosis. Factor or treatment by covariate interaction tests will be computed. Hazard Ratios with 99% confidence intervals will be tabulated. Forest Plots will be presented.

The distribution of MGMT promoter methylation status, 1p and 19q LOH in each histological diagnosis will be presented.

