8.2.5 Prognostic factor analyses

Prognostic factor (PF) analyses for overall survival are prospectively planned. The main PF analysis will include: both questions (I and II), clinical covariates (WHO Performance Status, Age, Extent of Surgery, Tumor location, Previous surgery for Low Grade Glioma), Presence of oligodendroglial component, 1p/19q LOH status and MGMT promoter methylation status, histopathology parameters and biomarkers available at the time of analyses.

In the univariate stage, depending on its scale, each question and covariate will be screened by an appropriate two-sided logrank test (heterogeneity or trend). Kaplan-Meier curves will be computed. The Peto' interaction test will be computed between questions and between questions and covariates. Main effects and interactions with $p < 0.15$ will be considered for inclusion into the multivariate modeling stage. If an interaction is detected the main effects and interaction term will be included in the multivariate models. Variables will be included with their full categorization, no regrouping or selection of categories is allowed.

All selected covariates will be included into a multivariate Cox proportional hazards model. Both the automatic backward and stepwise selection method (significance to enter and/or stay in the model at 0.05) will be tested. The differences between the two selection methods will be documented. Nevertheless, in case of discrepancies, the selection of main effects and interactions provided by the stepwise selection method will be considered for the final model. As an internal validation, the bootstrap resampling technique will be used to estimate the probability of inclusion of each main effect or interaction term in Cox proportional hazards models with stepwise selection at 5% significance and identified the 10 models with the variables selected with the highest frequency. Only main effects or interactions with more than 60% probability of inclusion will be included in the final model.

If the final model of the main PF analysis includes interactions, additional models might be fitted in each question and/or chemotherapy arm separately applying the methodology described above.

The calibration, discrimination ability (Harrell's C-index) and Akaike's criteria (AIC) of final models will be estimated. Bootstrap technique will be used to correct parameters for "optimism" (Ref. 25).

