17.3.2.3 Central review for MGMT

MGMT central testing requires shipment of a tumor sample to the central Laboratory. MGMT status determination may be time consuming and may therefore not be compatible with the maximum time to elapse between diagnosis and start of radiotherapy which is of 7 weeks. The central facility will be set up but central MGMT status determination will not be made mandatory during the first year to test the feasibility. If central testing for MGMT is deemed to be feasible, it will be enforced for the rest of the trial. Regardless, it will be tried to determine MGMT determination prior to study entry in all patients.

The material requested for MGMT testing will be sent by the central histopathology laboratory in Rotterdam to MDxHealth (Liège, Belgium).

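### The undeterminate MGMT level mainly marks a missing result; read literally, section 8.2.5 gives it a degree of freedom in the MGMT-by-treatment interaction screen, which can cost up to about 9 points of power

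*Combined protocol and SAP*

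**What the plan says.** **Three levels at randomization.** Section 8.1.2 minimizes on "MGMT promoter methylation status (methylated vs unmethylated vs indeterminate"). Section 17.3.2 explains the third level: patients who lack a result "because of insufficient material, material not timely received etc will still be eligible for the study (and will be stratified for MGMT status as" a separate level, called undeterminate. Appendix K calls the same level unknown. Section 17.3.2.3 adds a further possible source, since "central MGMT status determination will not be made mandatory during the first year to test the feasibility".

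**Interaction tests.** Section 8.2.4.2 (exploratory analyses) repeats all comparisons within MGMT strata and adds: "Factor or treatment by covariate interaction tests will be computed". It gives no coding for undeterminate cases, no degrees of freedom and no significance level. Section 8.2.5 (prognostic factors) applies the Peto interaction test between questions and covariates, takes forward interactions with p<0.15, and then says: "Variables will be included with their full categorization, no regrouping or selection of categories is allowed".

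**MGMT in the analysis.** Section 8.2.3.2 already plans a secondary Cox analysis that uses MGMT status after randomization. Section 8.3.2 records an IDMC recommendation to obtain MGMT status for all patients, re-testing samples where needed, and to examine heterogeneity across subgroups.

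**The concern.** The scientific question about MGMT is whether the effect of temozolomide differs between methylated and unmethylated tumors. Section 1.1.2 motivates it: in glioblastoma the benefit of combined treatment "may be limited to patients whose tumors have a methylated (and thus silenced) MGMT gene promoter". A group with no result, if it is a mixture of the two tumor types, carries no information on that contrast. A three-level heterogeneity test nevertheless spends a degree of freedom on it, so the critical value rises while the signal stays the same.

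A real MGMT interaction could then fail the screen that decides whether it enters the multivariate model in 8.2.5. In 8.2.4.2, where the coding is left open, the choice between two and three levels could be made after subgroup results are known.

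**Working it through.** **1. The plan's own figure.** Section 8.1.1 states that, "based on a two-sided logrank test", "at an overall significance level of 5% and a power of 83%, a total of 534 events are needed", for HR 0.775. Schoenfeld's formula gives 4(1.960 + 0.954)²/(ln 0.775)² = 523 events. Adding the 11 events for the interim look gives 534, as stated. The plan gives no power for any MGMT interaction.

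**2. Inputs.** From the plan: 534 deaths. Assumed, because the plan is silent: undeterminate share u, with the other cases half methylated and half unmethylated; a treatment HR in each tumor type; undeterminate cases with the same half-and-half mix. The variance of a log HR in a stratum with d deaths is taken as 4/d.

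**3. Formulas.** Let b be the log HR in a stratum.
- 1 df: λ₁ = (b_meth − b_unmeth)² / (4/d_meth + 4/d_unmeth).
- 2 df: λ₂ = Σ (d_k/4)(b_k − b̄)², where b̄ is the information-weighted mean over the three levels.

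Under the half-and-half mix, the undeterminate log HR equals b̄, so it adds nothing and λ₂ = λ₁. Only the critical value changes: from 3.84 to 5.99 at 5%, and from 2.07 to 3.79 at 0.15.

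**4. One case in full.** Take u = 25%. Determined deaths are 0.75 × 534 = 400.5, or 200.25 per type. For HR 0.60 (methylated) and 0.95 (unmethylated), λ = (ln 0.60 − ln 0.95)²/(8/200.25) = 0.2112/0.03995 = 5.29. Noncentral chi-square power is 63.3% (1 df) against 52.8% (2 df) at 5%, and 80.5% against 72.5% at 0.15.

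**5. Other effect sizes, u = 25%.** Losses are in points, taken before rounding.

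| HR meth / unmeth | 1 df vs 2 df at 0.15 | Loss | 1 df vs 2 df at 5% | Loss |
|---|---|---|---|---|
| 0.63 / 0.90 | 63.6% vs 54.8% | 8.8 | 43.0% vs 33.9% | 9.1 |
| 0.60 / 0.95 | 80.5% vs 72.5% | 8.0 | 63.3% vs 52.8% | 10.5 |
| 0.60 / 1.00 | 86.8% vs 80.0% | 6.8 | 72.4% vs 62.3% | 10.1 |
| 0.55 / 1.00 | 94.0% vs 89.5% | 4.4 | 84.9% vs 76.8% | 8.1 |
| 0.50 / 1.00 | 97.9% vs 95.7% | 2.2 | 93.4% vs 88.4% | 5.0 |

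Over all noncentralities the largest loss is 8.8 points at 0.15 (1-df power about 68%) and 10.5 points at 5% (1-df power about 63%). With u from 10% to 40%, a methylated share of 40–50%, and HR pairs from 0.63/0.90 to 0.50/1.00, the loss runs from 1.2 to 8.8 points at 0.15 and from 3.2 to 10.5 points at 5%.

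**6. A small undeterminate group does not remove the cost.** For HR 0.60/0.95 with u = 10%, power at 5% is 71.2% against 61.0%, a loss of 10.2 points. The degree of freedom is spent for as long as the level exists.

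**7. If the undeterminate mix differs.** For HR 0.55/1.00, u = 25%, at 5%, the 1-df power is 84.9%. The 2-df power is 76.8% at a 50% methylated mix, 79.4% at 25% or 75%, and 85.9% if the group is all one type. The loss falls from 8.1 to 5.5 points and then becomes a gain of 1.0.

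**8. Simulation check.** With 748 patients, analysis at 534 deaths, exponential survival and 5,000 runs, HR 0.55/1.00 with u = 25% gave 83.8% against 75.7% at 5%. With no treatment effect in either tumor type, rejection rates were 4.9% (1 df) and 5.1% (2 df), so size is not the issue.

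**The case against.** Several points on the other side stand.

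- **A flat loss of 8 to 11 points.** A reader might infer this, but the documents do not support it. They give no undeterminate share, no MGMT split and no MGMT-specific effect, and the loss varies with all of these. The interaction screen under the explicit category rule runs at 0.15, where the loss never exceeds 8.8 points.
- **The trial's main marker question.** A reader might call it that. The plan does not: 8.2.4.2 is headed exploratory, 8.2.5 is prognostic modelling, and IDH1 has its own secondary Cox analysis in 8.2.3.2.
- **A mandated 2-df test throughout.** Section 8.2.4.2 does not say so; a methylated-versus-unmethylated test would comply with it. Even in 8.2.5 the category rule follows the sentence on multivariate inclusion, so its reach back to the screen is a literal reading, not an explicit instruction.
- **Undeterminate as purely no result.** The list of reasons in 17.3.2 is open-ended, and section 4 lists indeterminate among the statuses that the data center reports. An equivocal assay result is not excluded.
- **Re-testing.** The IDMC recommendation in 8.3.2 targets the missing results, and 17.3.2.3 aims at determination in all patients. If every patient is resolved, the cost is zero.

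The planned stratum HRs would also let a reader form the 1-df contrast by hand. None of this makes the three-level test the better default. Re-testing is a recommendation that depends on available tissue, and lack of tissue is a stated reason for the missing results.

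**Conclusion.** The point holds as a cheap improvement to secondary and exploratory analyses. Read literally, 8.2.5 makes the question-by-MGMT screen a 2-df test; in 8.2.4.2 the coding is open. If undeterminate cases are a random mix, this costs up to about 9 points of power at the 0.15 screen. For a test at 5% it costs up to about 10. The 5% figure is relevant because 8.2.4.2 states no level and 8.2.5 later uses 0.05 for model entry and stay; the calculation does not model that selection procedure.

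The size rests on assumed interaction effects and an assumed undeterminate mix, neither of which the documents give. Primary inference on the two treatment questions is untouched, and type I error is not inflated.

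**What to change.** In 8.2.5 and 8.2.4.2, state that the MGMT-by-question interaction is the 1-df contrast of methylated versus unmethylated among patients with a determined status, using the MGMT status determined after randomization, as 8.2.3.2 already does. In 8.2.5, apply this to the p<0.15 screen and exempt the undeterminate level from the category rule for this test.

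Keep undeterminate as a level for minimization and main-effect adjustment, and report its HR descriptively.

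The cost is a few sentences of SAP wording. The small downside is that patients with undeterminate status do not contribute to the interaction test. Under a random mix they carry no information on it; if the group were nearly all one tumor type, a little power would be given up (about 1 point in the example above).
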